Procedure or Assessment	Screening (Day -30 to Day -1)	W1D1	W2D1	W4D1	W4D2	Q3W (W7D1, W10D1, etc.)	End of Treatment (EOT) ^a	30-Day Safety Follow-up (30DFU) ^b	Posttreatment Follow-up (PTFU) ^c (Q3mo)	Long-Term Survival Follow-up (LTSFU) ^d (Q3mo)
Visit Windows	n/a	n/a	-2/+5d	+3d	n/a	± 3d	+7d	+7d	± 2 weeks	± 4 weeks
CMP-001 Injection (Dose Number) ^e		1 SC/IT	2	3		4+				
Pembrolizumab Dosing (Dose Number) ^f		1		2		3+				
Thyroid Function Tests ^l	X			X		X	X			
Autoimmune Laboratory Panel ^l	X						X			
Pregnancy Test and Follicle Stimulating Hormone ^l	X	X		X		X	X			
Exploratory Biomarker Sampling ^m		X		X	X	W7D1				
Exploratory Sampling for Pharmacokinetics ^m		X		X	X	W7D1				
Tumor Biopsy (known PD-L1 status) ⁿ	X					W7D1				
Blood Sampling for Cytokine and Complement ^o		X		X		W7D1				
Disease Assessment (Radiographic Imaging) ^p	X					W10D1 Q9W	X		X	
Disease Assessment (CNS Imaging) ^p	X					W10D1 Q9W	X		X	
Photographic Imaging ^q	X					W10D1 Q9W	X		X	
30-Day Follow-Up (Office or Phone Call)								X		
Long-Term Survival Follow-up Phone Call										X

Abbreviations: 30DFU = 30-day follow-up; CNS = central nervous system; CPS = combined positive score; D = day; ECG = electrocardiogram; ECOG = Eastern Cooperative Oncology Group; EOT = end of treatment; FSH = follicle stimulating hormone; HPV = human papillomavirus; iRECIST = immunotherapy Response Evaluation Criteria in Solid Tumors; LTSFU = long-term survival follow-up; MRI = magnetic resonance imaging; PTFU = posttreatment follow-up; RECIST = Response Evaluation Criteria in Solid Tumors; Q3W = every 3 weeks; W = week; WOCBP = women of child bearing potential.

a. EOT assessments to be performed within 7 days following subject discontinuation from study treatment. Removal of a subject from CMP-001 treatment is defined as the time in which the Investigator decides to discontinue study treatment. If a subject has CMP-001 dosing withheld for more than 3 consecutive doses for any reason during the Q3W dosing period, resumption of treatment must be discussed with the Medical

Amendment 2 (Version 3.0)

14 January 2022

13

Confidential

Monitor; otherwise, the subject will be discontinued from study treatment and will have all EOT assessments performed. End of Treatment occurs once the subject discontinues administration of CMP-001. Subjects can continue to receive pembrolizumab as standard of care but will no longer be considered in study treatment.

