- b. The 30-Day Follow-up is a safety follow-up visit that may be conducted in the study clinic OR via phone. This visit should occur 30 days (+7) after the EOT visit.
- c. PTFU will be conducted every 3 months (\pm 2 weeks) for all subjects who discontinue study treatment but have not met criteria for study discontinuation. These subjects should remain on study and receive disease assessments every 3 months, until discontinuation.
- d. LTSFU will be conducted every 3 months (\pm 4 weeks) after the EOT visit or the last disease assessment date in PTFU and may occur by phone call.
- e. CMP-001 Injection Visits: Weekly Dosing (W1D1 and W2D1): The first dose of CMP-001 may be administered SC or IT, at the discretion of the Investigator; all subsequent doses are planned to be administered IT until no injectable lesions remain. A window of $-2/+5$ days is permitted for CMP-001 dosing on W2D1. Q3W Dosing (W4D1+): A window of ± 3 days is permitted for CMP-001 dosing from W4D1 throughout the trial. When pembrolizumab is permanently discontinued, CMP-001 must also be permanently discontinued. Refer to Section 5.4 for Treatment Compliance.
- f. Pembrolizumab dosing will begin on W1D1 and continue Q3W throughout the study. When CMP-001 injection and pembrolizumab dosing fall on the same day, the CMP-001 injection will be given before pembrolizumab dosing. Refer to Section 5.1.1 for Pembrolizumab Dosing.
- g. A full PE will be conducted at Screening and EOT. If the Screening full PE is performed > 72 hours before the W1D1 visit, then a brief (symptom directed) PE must be performed within 72 hours before the first injection of CMP-001. Brief PEs focused on areas of disease or AEs must be performed at every CMP-001 injection visit, and at any other time as clinically indicated. Height will be obtained at Screening only and weight at all PE assessments.

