4.7. End of Clinical Trial

The End of Clinical Trial (EOT) is defined as the last visit for the last subject on the trial. All data collection will cease in all subjects when End of Clinical Trial is reached.

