7.7. Long-Term Survival Follow-Up

Subjects who discontinue study treatment and PTFU, will be contacted by the site according to the Schedule of Assessments ([Table 1](#)) for LTSFU, which will continue until death, withdrawal of consent, lost to follow-up, or End of Clinical Trial.

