C. Sample Size Status

Given the early termination of site activation and study enrollment since 24Jun2022 per Sponsor's decision, all the analyses will be descriptive and exploratory. The number of subjects included in this study is 24. Subjects who have provided written informed consent once the enrollment goal is reached may be allowed to complete Screening and enter study treatment if they meet all eligibility criteria, at the discretion of the Sponsor or its representatives. As enrollment is terminated, subjects who discontinue the study before receiving the first dose of CMP-001 will not be replaced.

With the enrollment of the last subject on 22Jun2022, the subject status of this study is as follows:

- 39 subjects were screened
- 15 subjects were screen failures
- 24 subjects started the treatment

D. Treatment Randomization

No randomization will be performed in this study.

E. Assessment Schedule

See Protocol Table 1 for the study schedule of assessments.

F. End of Study

Per Sponsor's decision, site activation and study enrollment were terminated officially on 24Jun2022. All subjects previously enrolled in the study may continue receiving up to 2 years of study treatment per the current protocol.

The end of study is defined as the date of the last dose of study treatment for the last ongoing subject, plus 30 days of safety follow-up.

III. Protocol Objectives

Per Sponsor's decision, enrollment was stopped before reaching the sample size planned for the analyses described in the Protocol. All analyses will be exploratory. The performance of the statistical analysis for the protocol objectives and endpoints of the exploratory phase 2 study is contingent on the availability of the data source. Detailed information will be provided in the corresponding sections to follow.

Regeneron Pharmaceuticals Inc. / Protocol: CMP-001-007
IQVIA Biotech (Confidential) Project # SZA56629

A. Primary

- To determine the Investigator-assessed confirmed objective response with CMP-001 in combination with pembrolizumab in subjects with head and neck squamous cell carcinoma (HNSCC).

B. Secondary

- To evaluate the safety and tolerability of CMP-001 administered by intratumoral (IT) injection in combination with pembrolizumab in subjects with HNSCC.
- To evaluate the efficacy of CMP-001 in combination with pembrolizumab in subjects with HNSCC.

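### The SAP's end of study (last dose plus 30 days) conflicts with the protocol's end of trial, and OS Table 1c can censor living subjects at a date later than their last known survival status

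*SAP*

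**What the plan says.** **SAP II.F (End of Study):** "The end of study is defined as the date of the last dose of study treatment for the last ongoing subject, plus 30 days". The sentence goes on to call those 30 days safety follow-up. Posttreatment follow-up (PTFU) and long-term survival follow-up (LTSFU) are not mentioned.

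**Protocol 4.7:** "The End of Clinical Trial (EOT) is defined as the last visit for the last subject on the trial". It adds: "All data collection will cease in all subjects when End of Clinical Trial is reached". The abbreviation EOT is used there for the end of the trial. Elsewhere, and below, it means the end-of-treatment visit.

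**Protocol 7.6 and 7.7:** PTFU scans run until progression, new therapy, death, loss, withdrawal or the end of the trial. LTSFU contacts are ones "which will continue until death, withdrawal of consent, lost to follow-up, or End of Clinical Trial".

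**SAP II.A:** subjects off treatment who have not met study discontinuation criteria stay on study for PTFU and LTSFU.

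**Protocol Table 1, notes a and b:** "EOT assessments to be performed within 7 days following subject discontinuation from study treatment"; and for the 30-day safety follow-up, "This visit should occur 30 days (+7) after the EOT visit". Note d sets LTSFU every 3 months with a window of 4 weeks either way, and allows it by phone.

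**OS censoring:** the OS paragraph in SAP VIII.A uses the date last known alive or data cutoff, whichever is first. Table 1c uses the study completion date if the study was completed before cutoff, and the cutoff date if the study is continuing. It uses the date last known alive only for subjects lost to follow-up.

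**The concern.** The two documents give different events as the end of the study, and the SAP is also at odds with its own design section. The SAP date depends only on one subject's last dose. It therefore need not include that subject's 30-day safety visit, and it takes no account of when the other subjects were last contacted.

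The statistical consequence lies in OS. A subject in LTSFU may last have been confirmed alive months before the study closes. If that subject is censored at a study completion or cutoff date, the interval since the last contact is counted as observed survival although nobody checked. A death in that interval goes unseen, so the error runs toward longer survival. If the subject is censored at the date last known alive, no such credit is given. The SAP specifies both rules.

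**Working it through.** The plan gives no figure to reproduce, so the check is date arithmetic followed by a rough size for OS.

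**1. SAP end against the last subject's 30-day visit.** Day 0 is that subject's last dose.
- SAP end: day 30 (SAP II.F).
- 30-day visit: gap from last dose to the decision to stop + EOT window (0 to 7) + 30 + visit window (0 to 7). The gap is not stated; 0 to 21 days (one 3-weekly cycle) is assumed.

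| Gap | 30-day visit, earliest | Latest | SAP end is earlier by |
|---|---|---|---|
| 0 days | 0 + 0 + 30 + 0 = day 30 | 0 + 7 + 30 + 7 = day 44 | 0 to 14 days |
| 21 days | 21 + 0 + 30 + 0 = day 51 | 21 + 7 + 30 + 7 = day 65 | 21 to 35 days |

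The dates coincide only if the EOT visit is on the day of the last dose and no visit window is used.

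**2. Adverse event window.** Protocol 7.4.1 and Table 1 note i collect adverse events to 30 days after last dose. Day 30 covers this, reading study treatment as both drugs.

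**3. That subject's first later contacts.** Taking 3 months as 91.3 days from EOT and no gap:
- first LTSFU contact: 91.3 − 28 = day 63 at the earliest;
- first PTFU scan: 91.3 − 14 = day 77 at the earliest.

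Both fall after day 30.

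**4. Age of survival status in LTSFU.** Up to one interval plus its window: 91.3 + 28 = 119 days, or 119/30.4375 = 3.9 months. Hence 3 to 4 months at worst.

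**5. Size for OS.** Inputs:
- median OS 14.9 months (Protocol 1.1, pembrolizumab monotherapy);
- exponential survival (assumed), so the hazard is ln 2/14.9 = 0.0465 per month;
- 15.1 to 16.9 deaths among 24 by the SAP end. This comes from a simulation with response rate 19% to 35%, median responder duration 20.9 months (Protocol 1.1), assumed non-responder median treatment of 2.5 to 4 months, assumed accrual of 12 to 20 months, and treatment capped at 24 months and at death.

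This leaves 24 − 16.9 = 7.1 to 24 − 15.1 = 8.9 subjects alive.
- *Extending from day 30 to day 65:* 35/30.4375 = 1.15 months. Expected extra deaths = alive × (1 − e^(−0.0465 × 1.15)) = alive × 0.052 = 0.37 to 0.46. Simulation gives about 0.4 to 0.5.
- *Deaths unseen because status is old:* alive × (e^(0.0465 × t) − 1). With t = 1.5 months (half an interval, an average case), alive × 0.072 = 0.51 to 0.64. With every status 3 months old, alive × 0.150 = 1.1 to 1.3. Simulation of a closing contact gives about 0.7.

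Together about 0.4 + 0.7 = 1.1, roughly 1 death of about 16.

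**6. Potential follow-up.** If the subject enrolled on 22 June 2022 is the last ongoing one and is treated for 2 years, the SAP end is 22 July 2024, about 25 months after enrolment. If that subject is the last ongoing one and stops at 12 months, it is about 13 months.

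**The case against.** Much of the case on the other side stands.

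- *The SAP governs analysis, not conduct.* SAP I.B gives it precedence only for data analysis and warns of differences from the protocol. SAP II.A keeps PTFU and LTSFU, and Table 2 still draws on both follow-up forms. A reader might infer from II.F that follow-up of all 24 subjects is cut short. The SAP does not say that, and subjects already dead, withdrawn or lost have nothing left to lose.
- *PFS and DOR rules do not use this date.* Tables 1a and 1b depend on data cutoff, last assessment, new therapy, missed assessments and loss or withdrawal. Only Table 1c refers to study completion, and the SAP never links that term to II.F. It might mean an individual subject's completion.
- *There is no protocol benchmark for early.* LTSFU runs until the end of the trial, and the trial ends at the last visit. That is circular and sets no minimum follow-up. Restoring 4.7 alone would not tie follow-up to endpoint maturity.
- *A large loss of deaths.* A reader might compare the SAP end with 27 months after last enrolment. Simulation then gives 18.6 to 19.4 deaths against 15.1 to 16.9, a gap of 2 to 4. No document sets 27 months, and waiting that long would delay closure by about 7 to 13 months at the median. That is a separate trade-off.
- *The analyses are exploratory.* SAP II.C makes every analysis descriptive after enrolment stopped.

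What remains is that the definitions conflict and that the two OS censoring rules differ. The precedence clause cannot settle a conflict within the SAP.

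**Conclusion.** The point holds as an inconsistency with a modest effect on exploratory OS. SAP II.F and Protocol 4.7 define different end dates, and II.F fits poorly with SAP II.A. The SAP date precedes the last subject's 30-day visit by 0 to 35 days and always precedes that subject's first PTFU scan and LTSFU contact. The statement that the safety visit is always missed would be too strong, because the dates can coincide and the 30-day adverse event window is covered.

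The OS effect is roughly 1 death of about 16. It assumes exponential survival with the 14.9-month median, the assumed accrual and treatment durations, and use of the SAP date as the study completion or cutoff date in Table 1c. A loss of 2 to 4 deaths is not supported. ORR is unaffected, and no PFS or DOR censoring rule refers to II.F. The correction is worth making because it is cheap and makes OS censoring more accurate.

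**What to change.** 1. Reconcile Protocol 4.7 with SAP II.A and II.F, and state which definition controls conduct and whether PTFU and LTSFU continue past last dose plus 30 days.
2. Define end of study as the later of (a) the last subject's 30-day safety visit, that is the EOT visit plus 30 to 37 days, and (b) one closing survival-status contact for every subject not known dead, withdrawn or lost. Make that contact on or after the last subject's last dose, and record the date last known alive and any new anticancer therapy.
3. In Table 1c, censor living subjects at the date last known alive, capped at data cutoff, so that it agrees with the OS text. Define study completion date or remove the term.

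The cost is revised wording, up to 24 contacts of a kind the protocol already allows by phone, a short instruction to sites, and a lock delay of about 1 to 2 months. No new procedure is needed. The change does not guarantee mature 12- or 18-month rates, which still depend on how long the last subject stays on treatment.

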Statistical analyses will be performed using SAS® software version 9.4 or higher. MedDRA version 23.1 will be used for the coding of Medical History and Adverse Events. AEs are graded using Common Terminology Criteria for Adverse Events (CTCAE) Version 5.0. World Health Organization Drug Dictionary (WHO-DD) version

Regeneron Pharmaceuticals Inc. / Protocol: CMP-001-007
IQVIA Biotech (Confidential) Project # SZA56629

B3 Global September 2020 (or later) will be used to code the Prior and Concomitant Medications, and Prior Cancer Systemic Treatments.

A. Data Sources

Data are recorded on electronic case report forms (eCRFs). Central laboratory data will be provided via electronic data transfers. Protocol Section 11 and the study Data Management Plan provide additional details regarding data recording and handling.

B. Definition of Baseline and Study Day

Baseline is defined as the last non-missing observation prior to the first administration of study drugs (CMP-001 or Pembrolizumab). Study Day 1 will be designated as the first day a subject receives either study drug (i.e., Week 1 Day 1).

C. Missing Data

Unless stated otherwise, missing data will not be replaced with imputed values. When relevant, sections below will address how missing data will be handled for the analyses.

Missing or Partial Death Dates

A death date missing the month and day will be imputed as Jan 1st of the year or the date after the date of last known alive, whichever comes last.

A death date missing the day will be imputed as the 1st of the month or the day after the date of last contact, whichever comes last.

Missing Dates in Adverse Events/Concomitant Medications

Every effort will be made to avoid missing/partial dates in on-study data including AE and medication start and stop dates.

Start dates of AEs/ Concomitant medications will be imputed as follows:

- Completely missing start date will not be imputed.
- Start date missing both the month and day will be imputed as:
 - The date of the first dose if the year of the start date is the same as the date of first dose.
 - Otherwise, Jan 1st of the year of the start date will be used.
- Start date missing the day will be imputed as:

Regeneron Pharmaceuticals Inc. / Protocol: CMP-001-007
IQVIA Biotech (Confidential) Project # SZA56629

- The date of first dose if the year and month of the start date are the same as the date of first dose.
- Otherwise, the 1st of the month of the start date will be used.

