Stop dates of AEs / Concomitant Medications will be imputed as follows:

- Completely missing stop date will not be imputed.
- Stop date missing both the month and day will be imputed as Dec 31st of the year of stop date.
- Stop date missing the day will be imputed as the last date of the month of the stop date.
- After imputation, the imputed date will be compared against the date of death, if available. If the planned imputed date is later than the date of death, the date of death will be used as the imputed date instead. If there is no date of death in the EDC for a subject and the planned imputed date is later than the End-of-Treatment (the last drug received) date + 30 days, then the End-of-Treatment (EOT of the last study drug received) date + 30 days will be used for the stop date.

Missing Dates in Prior Medications

Start or Stop dates of Prior Medications will be imputed as follows:

- Completely missing start or stop date will not be imputed.
- Start or stop date with missing both the month and day will be imputed as Dec 31st of the year of stop date.
- Start date missing the day will be imputed as the 1st of the month of the start date.
- Stop date missing the day will be imputed as the last date of the month of the stop date or the study first dose date, whichever comes earlier.

D. Multiple Study Centers

No adjustment for study center is planned.

E. Covariate Adjustment in Primary Analysis

No covariate adjustments are planned.

F. Sample Size Reassessment

Not applicable.

Regeneron Pharmaceuticals Inc. / Protocol: CMP-001-007
IQVIA Biotech (Confidential) Project # SZA56629

G. Ad-hoc Analyses

There will be an ad-hoc analysis planned with the trigger event being two disease assessments after the enrollment of the last subject. The ad-hoc analysis of the endpoints will follow the efficacy analysis methods described in Section **Error! Reference source not found.** below as well as the safety analysis methods detailed in Section **Error! Reference source not found.** below for the exploratory Phase 2 study.

The following unblinded subject information, efficacy-related and safety-related data displays will be produced for the purpose of the ad-hoc analysis. Unless stated otherwise, these displays are summary tables that summarize data for the corresponding analysis set:

- Subject information
 - Demographics
 - Baseline characteristics
 - Disposition
 - Medical history
 - Cancer history
 - ECOG
- Efficacy

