Adverse event (AE) data are available to the Sponsor from two sources, the eCRFs and the Serious Adverse Event (SAE) paper forms and corresponding SAE narratives. While reconciliation will be performed to ensure consistency between the two types of data, the production of data summaries and listings will be based on the data collected on the eCRF.

Treatment-emergent adverse event (TEAE)

Pretreatment AEs are AEs that occur from the time of informed consent up to the first dose of study treatment (W1D1). A treatment-emergent adverse event (TEAE) is defined as an AE that started or worsened in severity on or after the date that study treatment was first administered (W1D1) until 30 days after the last dose of

Regeneron Pharmaceuticals Inc. / Protocol: CMP-001-007
IQVIA Biotech (Confidential) Project # SZA56629

study treatment. AE data collection also ceases at the time a new cancer treatment is started per protocol section 8.3, whichever occurs first.

Treatment-emergent adverse events will be coded using MedDRA (version 23.1) and data will be summarized for the Treated Analysis Set. The number and percent of subjects reporting each TEAE will be summarized, as well as the number of TEAEs. A subject with 2 or more TEAEs within the same level of summarization (i.e., system organ class or preferred term) will be counted only once in that level using the most severe event or most related (for the relationship to study treatment tables).

AEs are graded using Common Terminology Criteria for Adverse Events (CTCAE) Version 5.0. AE summaries may include summaries for all AEs and by the maximum CTCAE grade for the item being summarized (i.e., SOC or PT). In these cases, the outputs will include a row for All Grades as well as rows for the 5 potential CTCAE grades: Grade 1 (Mild), Grade 2 (Moderate), Grade 3 (Severe), Grade 4 (Life threatening or disabling), or Grade 5 (Death).

If grade is missing for a TEAE, the event will be counted as grade 3=severe in the TEAE summary tables. If relationship is missing for a TEAE, the event will be counted as related in the TEAE summary tables. Therefore, related AEs include those which are definitely, probably and possible related and those with missing relationship.

A TEAE summary table will be generated including the following (N (%)):

- Subjects with TEAEs
- Subjects with TEAEs of grade 3 or higher
- Subjects with TEAEs Related to CMP-001 and/or Pembrolizumab
- Subjects with CMP-001-related TEAEs

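### SAP VI.C sets partial AE start dates to first dose without checking the stop date, and gives no treatment-emergent status to an AE with no start date

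*SAP*

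**What the plan says.** SAP VI.C opens with a general default: "Unless stated otherwise, missing data will not be replaced with imputed values". For AE start dates it then gives three rules.

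- No date at all: "Completely missing start date will not be imputed".
- Year only: "The date of the first dose if the year of the start date is the same as the date of first dose"; otherwise 1 January of the recorded year.
- Year and month only: the first-dose date if both match first dose; otherwise the first of the recorded month.

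A fully missing stop date is treated like a fully missing start date: "Completely missing stop date will not be imputed". Partial stop dates go to the end of the month or year, and are then capped at death or at end of treatment plus 30 days.

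SAP IX.B classifies events by date. A TEAE is "defined as an AE that started or worsened in severity on or after the date that study treatment was first administered", up to 30 days after the last dose. A pretreatment AE falls between consent and first dose. The gap-filling rules for severity and causality are worded for events that already have TEAE status: "If grade is missing for a TEAE, the event will be counted as grade 3=severe in the TEAE summary tables", and a missing relationship is counted as related. The AE overview and the tables by system organ class and preferred term stand under TEAE headings.

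**The concern.** There are two separate faults in the start-date rules.

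The first is a stated rule that can give an impossible result. The first-dose imputation looks only at the start date. If the recorded stop date is already before first dose, the rule still moves the start to first dose. A resolved pretreatment event then meets the TEAE definition.

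The second is an omission. Treatment-emergent status needs a date, a fully missing date stays missing, and no fallback is given. Two programmers could reasonably decide differently. The plain comparison with first dose would not flag the event, so it would not reach the incidence tables. The rules for missing grade and missing relationship would not reach it either.

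Safety is a secondary objective and the planned AE incidence tables are TEAE tables. The first fault can overcount and the second can undercount, so no net direction of bias is claimed. What is at stake is a TEAE flag that is reproducible and free of impossible date orders.

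**Working it through.** The documents state no figure on this point, so the check traces the rules and then sizes one affected subject.

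**Inputs.** Start- and stop-date rules: SAP VI.C. TEAE definition and table scope: SAP IX.B. Denominator: SAP II.C, 39 screened − 15 screen failures = 24 treated, which agrees with the stated 24. Screening window: Day −30 to Day −1 (Protocol Table 1), so consent and first dose can fall in the same month.

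**Date trace.** The dates are hypothetical: first dose 15 Mar 2022, last dose 1 Sep 2022.

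| Recorded start | Recorded stop | Start after VI.C | TEAE by date? |
|---|---|---|---|
| Mar 2022 | 10 Mar 2022 | 15 Mar 2022 | Yes, but it starts 5 days after it stopped |
| 2022 | 10 Mar 2022 | 15 Mar 2022 | Yes, same fault |
| Feb 2022 | any | 1 Feb 2022 | No |
| 2021 | any | 1 Jan 2021 | No |
| Sep 2022 | any | 1 Sep 2022 | Yes |
| none | any | none | Undetermined |

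In the first two rows the stop date alone shows that the event was over before treatment. If the stop day were missing as well (Mar 2022), VI.C would set the stop to 31 Mar 2022 and no clash would appear. The fault therefore needs a stop date that is known to precede first dose.

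**Does the worsening limb of the TEAE definition help the undated event?** No. SAP IX.B has a worsened AE reported again with its new grade, so that record depends on its own date.

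**Are cross-checks foreign to VI.C?** No. Imputed death dates are checked against the last date known alive or last contact. Imputed AE stop dates are checked against death and end of treatment plus 30 days. Day-missing stop dates of prior medications are checked against first dose. AE start dates have no such check.

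**Size.** A row with k affected subjects and no others reads k/24, with exact (Clopper-Pearson) 95% limits:

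- k = 0: 0% (0 to 14.2%); upper limit 1 − 0.025^(1/24) = 0.142
- k = 1: 1/24 = 4.2% (0.1 to 21.1%)
- k = 2: 2/24 = 8.3% (1.0 to 27.0%)
- k = 3: 3/24 = 12.5% (2.7 to 32.4%)

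The range 1 to 3 is an assumption. Subjects count once per system organ class or preferred term, so a row moves only if the subject has no other qualifying event in it. Rows for Grade 3 or higher, or for related events, move only if the event has that grade or attribution, or if that field is missing.

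**The case against.** The strongest reply is that the SAP never says an undated AE is dropped. A reader might infer that such an event is removed from every AE table, but the text supports only undetermined status. SAP IX.B and Protocol 7.4 send occurrences before treatment to the Medical History page, so an undated record on the AE page is presumptively post-dose. The by-subject AE listing, and the separate listings of SAEs and of AEs leading to discontinuation, are not stated to be limited to TEAEs. The deaths summary in SAP IX.C does not depend on AE onset. All of this stands.

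A reader might also infer that the SAP resolves every other AE gap in the worst-case direction, so that this rule is the one exception. That is not so. Missing grade becomes Grade 3, not 4 or 5, and a fully missing stop date is also left alone, in line with the general default.

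Controls exist too. The SAP states: "Every effort will be made to avoid missing/partial dates in on-study data including AE and medication start and stop dates". Protocol 8.3 requires onset date and time for every AE and also captures them on the paper SAE form. SAP IX.B reconciles that form with the eCRF, and Protocol 11.1 has discrepancies queried. The stop-date fault needs several things at once: a pretreatment event on the AE page, a partial start matching first dose, and a stop date before first dose. The analyses are descriptive and no safety threshold hangs on them.

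These points limit the size but do not close the gap. The Medical History routing is not watertight. SAP IX.B defines pretreatment AEs, Protocol 7.4.1 monitors procedure-related ones from consent, and Protocol 8.3.1 collects SAEs from consent. Pre-dose records can therefore sit on the AE page. The default that the routing suggests is not written down, and nothing in the routing stops the start-after-stop result.

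**Conclusion.** The point holds as a small correction. The first-dose imputation for partial AE start dates can turn an event that resolved before treatment into a TEAE with its start after its stop; this follows directly from the stated rule. Separately, the SAP gives no treatment-emergent status to an AE with no start date, and a literal date comparison would leave it out of the TEAE tables but not out of the listing.

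The effect is up to 4.2 percentage points per affected subject in a given row, and zero where that subject already counts in the row. The number of affected subjects is not in the documents and should be small. The conclusion assumes that the SAP's date rules are programmed as written and that some pre-dose events reach the AE page.

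**What to change.** Add two sentences to SAP VI.C, under the AE start-date rules:

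*The first-dose imputation for a partial AE start date is not used when the recorded stop date precedes first dose; such an AE is pretreatment. An AE with a completely missing start date is classed as treatment-emergent unless its stop date precedes first dose.*

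The second sentence assigns a status without inventing a date, so the no-imputation rule for fully missing start dates can stay. The rules for missing grade and missing relationship then apply to the undated event as they do to any other TEAE.

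The cost is two sentences and a small change to the derivation of the TEAE flag, with no new data. The downside is that an undated event that in fact began before treatment may be counted as a TEAE.
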